12.3 Adverse Events

AEs will be coded according to MedDRA® version 18.0 or higher.

An overall AE summary will be presented for the following pre-defined subsets of events:

- Any TEAEs
- Any TEAEs considered related to treatment
- Any TEAEs leading to study drug discontinuation
- Any SAEs
- Any deaths
- Any SAEs considered related to treatment
- Any SAEs leading to study drug discontinuation

Listings by subject will be presented for the following subsets:

- Any TEAEs

- Any SAEs

All TEAEs will be summarized and grouped by MedDRA® System Organ Class (SOC) and specific AE preferred term (PT). Results will be displayed in order of decreasing frequency by SOC and PT.

Summaries will also be produced of SAEs, treatment related AEs and TEAEs leading to study drug discontinuation by SOC and PT terms. In addition, a summary will be provided by severity (mild, moderate, severe).

For all summary tables, both number of events and number of subjects will be tabulated. For subjects, percentages will be calculated from the total number of subjects per treatment group. Related to treatment is defined as any adverse events considered either “possibly”, “probably” or “definitely” related to study drug.

Tables will be presented for the double blind and open-label phases separately.

In addition a cumulative summary will also be presented for all subjects on active treatment for all TEAEs, SAEs and TESAEs leading to discontinuation of study drug grouped by SOC and PT terms occurring in either the double blind or open-label phase.

For the purposes of the interim analysis reporting, an AE cut-off point will be defined as any AE starting on or before Visit 5.

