8.3 Safety Set

Safety analyses will be performed on the Safety Analysis Set, which includes all subjects randomized to treatment who take at least one dose of study medication. Subjects will be classified according to actual treatment received. This analysis set will be used for all safety analyses.

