9.2 Reporting of Phases

Unless otherwise specified, tables will be reported separately for the Double Blind and Open Label phases. Tables reporting the Double Blind phase will be presented by treatment group.

In addition, baseline demographic and history tables will include an Overall column.

Tables reporting data from the Open Label phases will be presented by the original Double Blind treatment group and will also include an 'All Circadin' group. Unless otherwise specified, the two Open Label phases will be reported in the same table. For the main analysis, the Open Label tables will only include data for Visit 5. On completion of the study, the open label tables will be re-run to include all data up to the end of the study.

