Table 14.2.17.4	SDQ Total Difficulties Score Change from Baseline at 13 Weeks Double Blind – MMRM Analysis including Prior Clonidine Use as a Factor	FAS Set
Table 14.2.18.1	SND Total Sleep Time and Change from Baseline – Double Blind - Descriptive Statistics by Final Dose	FAS Set
Table 14.2.18.2	SND Sleep Latency and Change from Baseline – Double Blind - Descriptive Statistics by Final Dose	FAS Set
Table 14.2.18.3	SND Duration of Wake and Change from Baseline – Double Blind - Descriptive Statistics by Final Dose	FAS Set
Table 14.2.18.4	SND Number of Awakenings and Change from Baseline – Double Blind - Descriptive Statistics by Final Dose	FAS Set
Table 14.2.18.5	SND Longest Sleep Period and Change from Baseline – Double Blind - Descriptive Statistics by Final Dose	FAS Set
Table 14.2.18.6	SND Total Sleep Time and Change from Baseline – Open Label - Descriptive Statistics by Final Dose	FAS Set
Table 14.2.18.7	SND Sleep Latency and Change from Baseline – Open Label - Descriptive Statistics by Final Dose	FAS Set
Table 14.2.18.8	SND Duration of Wake and Change from Baseline – Open Label - Descriptive Statistics by Final Dose	FAS Set
Table 14.2.18.9	SND Number of Awakenings and Change from Baseline – Open Label - Descriptive Statistics by Final Dose	FAS Set
Table 14.2.18.10	SND Longest Sleep Period and Change from Baseline – Open Label - Descriptive Statistics by Final Dose	FAS Set
Table 14.2.19	Summary of Level of Agreement between Sleep and Nap Diary and Actigraphy Assessment of Responder	FAS Set
Table 14.3.1.1	Summary of Study Drug Exposure	Safety Set
Table 14.3.1.2	Summary of Study Drug Modifications	Safety Set
Table 14.3.1.3	% Compliance by Scheduled Visit	Safety Set
Table 14.3.1.4	Dosage Achieved by Scheduled Visit	Safety Set
Table 14.3.1.5	Number of Dropouts -Chi-Square Test	Safety Set
Table 14.3.2.1	Summary of TESS by Scheduled Visit	Safety Set

Table Number	Table Title	Population
Table 14.3.2.2	Overall Adverse Event Summary: Double Blind Phase	Safety Set
Table 14.3.2.3	Overall Adverse Event Summary: Open Label Phase	Safety Set
Table 14.3.2.4	Treatment Emergent Adverse Events by System Organ Class and Preferred Term: Double Blind Phase	Safety Set
Table 14.3.2.5	Treatment Emergent Adverse Events by System Organ Class and Preferred Term: Open Label Phase	Safety Set
Table 14.3.2.6	Serious Adverse Events by System Organ Class and Preferred Term: Double Blind Phase	Safety Set

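### Read literally, the SAP divides open-label adverse event counts by the full Safety Set, including children who never took an open-label dose, so non-zero open-label subject percentages come out too low whenever a child leaves early

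*SAP*

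**What the plan says.** Five parts of the SAP bear on the denominator.

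- **SAP 12.3 (Adverse Events)** gives the percentage rule for all AE summary tables: "For subjects, percentages will be calculated from the total number of subjects per treatment group". The section then splits the output by phase: "Tables will be presented for the double blind and open-label phases separately". No second denominator is given for the open-label tables.
- **SAP 8.3 (Safety Set)** defines the set as one that "includes all subjects randomized to treatment who take at least one dose of study medication", and adds: "This analysis set will be used for all safety analyses". No open-label dose is needed to belong to it.
- **SAP 16.1 (List of Tables)** assigns all six open-label AE tables (14.3.2.3, .5, .7, .9, .11 and .13) to the Safety Set. An example is Table 14.3.2.5, "Treatment Emergent Adverse Events by System Organ Class and Preferred Term: Open Label Phase".
- **SAP 9.2 (Reporting of Phases)** fixes the columns: "Tables reporting data from the Open Label phases will be presented by the original Double Blind treatment group". An 'All Circadin' column is added, but its membership is not defined. By default both open-label phases share one table.
- **SAP 10.1 (Subject Disposition)** says who has started each open-label phase, by supply of drug at Visit 4 or Visit 5. It uses this for disposition only and does not link it to any analysis set or AE denominator.

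**The concern.** A child who withdraws during the double-blind phase and takes no open-label drug cannot have an open-label event, yet still counts in N. The numerator comes from those who entered open label and the denominator from everyone dosed since randomisation. The error runs in one direction: a non-zero subject percentage can be too low but never too high.

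The open-label period supplies the plan's longer-term safety data on active drug. Under SAP sections 1 and 13, the results to Week 28 go to regulators in support of approval, so these percentages are submission figures. The plan also treats dropout that differs by arm as a real possibility, since it tests for it (SAP 11.2.5). If more children leave one arm before Visit 4, the two original-arm columns are scaled down by different amounts and a difference can appear where none exists.

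**Working it through.** **Inputs.** The plan states no AE percentage, so there is none to reproduce. The figures that enter are 120 children randomised 1:1, hence 60 per arm, and at least 90 expected to complete Visit 5 (SAP 6.2). The 90 is twice the 45 per group in SAP 6.1. That figure does reproduce: with a difference of 0.72 − 0.27 = 0.45 h, SDs of 0.69 and 0.45 and a two-sided 5% level (sidedness assumed), an unequal-variance t-test with 45 per group has 95.1% power. This only confirms where the 90 comes from.

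Three further assumptions are needed: every randomised child takes at least one dose, so the Safety Set is 120; the number lost before open label lies between 0 and 120 − 90 = 30; and the true AE rates are illustrative.

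**Formula.** Let N be the Safety Set in a column, E the number of those who entered open label, and p the true percentage among the E.

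- Shown percentage = p × E / N
- Relative understatement = 1 − E / N
- Correction factor = N / E

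**Pooled column, N = 120.**

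| Not entering | E | E/N | True 10% shown as | True 20% shown as | True 30% shown as |
|---|---|---|---|---|---|
| 0 | 120 | 1.00 | 10.0% | 20.0% | 30.0% |
| 6 | 114 | 0.95 | 9.5% | 19.0% | 28.5% |
| 12 | 108 | 0.90 | 9.0% | 18.0% | 27.0% |
| 18 | 102 | 0.85 | 8.5% | 17.0% | 25.5% |
| 24 | 96 | 0.80 | 8.0% | 16.0% | 24.0% |
| 30 | 90 | 0.75 | 7.5% | 15.0% | 22.5% |

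In counts, at the upper end, 18 children with an event are shown as 18/120 = 15.0%, against 18/90 = 20.0% of those who entered. The correction factor there is 120/90 = 1.33.

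**Unequal loss by arm, 60 per arm, true rate 20% in both.** If 3 leave one arm and 12 the other (assumed), the expected displays are 0.20 × 57/60 = 19.0% and 0.20 × 48/60 = 16.0%. The gap of 3 percentage points comes only from the denominators.

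**Does another section override the literal rule?** SAP 9.1 sets a general default that also divides by the total number of subjects. Where the SAP wants a narrower base it states one: SAP 12.7 bases seizure percentages on children with an epilepsy diagnosis. No such statement exists for open-label AEs.

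**The case against.** The strongest reply is that SAP 12.3 speaks of the treatment group, not of the Safety Set by name, and that SAP 8.3 and SAP 12 classify children by the treatment they actually received. A child with no open-label drug has no open-label treatment, so a programmer could fairly use a phase-specific N, above all for 'All Circadin'. That is a possible practice, but it is not what is written. Classification by actual treatment decides which column a child belongs to, not who is counted in a phase, and SAP 9.2 keeps the open-label columns by original arm.

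A second reply is that the harm is limited. Both event and subject counts are tabulated, SAP 10.1 reports how many children start each open-label phase, and AE reporting is descriptive. This stands: a reader with both tables can rescale a percentage closely, and no hypothesis test is touched. It limits the importance of the point but is no reason to print a figure that needs rescaling.

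Three stronger readings are tempting and should not be drawn.

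- A reader might infer that every open-label rate is understated by a known amount. Zero percentages, event counts and any column in which nobody left early are unaffected, and the documents do not fix the size.
- A reader might infer that the cumulative tables (14.3.2.14 to .16) share the fault because they too are listed on the Safety Set. The text of SAP 12.3 and the table titles already restrict them to children on active treatment, so only the population label needs aligning.
- A reader might infer that the Week 28 cut-off, "an AE cut-off point will be defined as any AE starting on or before Visit 5", discards events in children who left before Visit 5. Nothing in the SAP says so. The cut-off serves reporting at the end of the first open-label period and has no bearing on denominators.

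**Conclusion.** The point holds as a literal reading of SAP 12.3, 8.3, 9.2 and 16.1 taken together. It applies to the subject percentages in Tables 14.3.2.3, .5, .7, .9, .11 and .13. The relative understatement in a column equals the fraction of its Safety Set that never entered open label. I put this at 0 to 25% as an assumed range for the pooled column, or for each arm if loss is equal; with unequal loss a single arm could exceed it.

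The upper end is unlikely for the first open-label phase. The fall from 120 to 90 runs to Visit 5, so 25% would require every expected loss to occur before any open-label dose. The effect is nil if nobody leaves before then. The double-blind tables and the primary analysis do not depend on this rule. The change is worth making because the written rule gives a figure biased in the favourable direction in a regulatory report and is simple to correct.

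**What to change.** In SAP 12.3, state N by phase:

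- **Double-blind tables:** Safety Set by arm, as now.
- **Open-label tables:** Safety Set children with at least one open-label dose, by original arm. Where the first and second open-label phases are shown separately, give each its own N, counting children with at least one dose in that phase. A dose is a better criterion than the supply rule in SAP 10.1, because a child can be supplied and never dosed.
- **'All Circadin' column in these tables:** the same basis, defined explicitly.
- **Cumulative tables 14.3.2.14 to .16:** align the population label in SAP 16.1 with the existing text, as children with at least one Circadin dose.

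The cost is a few lines of SAP text and a changed denominator in the AE programs. SAP 12.1 already needs the first open-label dose date; a date of first dose after Visit 5 would have to be derived if the second phase is shown separately. No new data are collected and the design does not change. Where children left before open label, the reported open-label percentages become slightly higher, and so less favourable.

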4.1 Primary Endpoint

- The primary efficacy parameter is TST time as assessed by a Sleep and Nap Diary after the 13-week, double-blind treatment period.

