4.3 Exploratory Endpoints

- Sleep variables as assessed by the Sleep and Nap Diary at baseline (Week 2), after 3 weeks of double blind treatment (Week 5), and after 13, 26, and 39 weeks of open-label treatment (Weeks 28, 41, and 54)
- Sleep disturbance as assessed by the CSDI score at baseline after 3 weeks of double-blind treatment (Week 5), after 13, 26, 39, and 91 weeks of open-label treatment (Weeks 28, 41, 54, and 106, respectively), and at the end of study visit (Week 108)
- Social functioning at home, in school, and in community settings as assessed by the CGAS after 13 weeks (Week 28) of open-label treatment
- Behavior at home and in school as assessed by the SDQ after 13 weeks (Week 28) of open-label treatment
- Caregiver's daytime sleepiness (i.e., NOT the child's) during the study as assessed by the ESS (Weeks 0, 2, 5, 15, 28, 41, 54, 106 and 108)
- Caregiver's well-being (i.e., NOT the child's) during the study as assessed by the WHO-5 questionnaire (Weeks 0, 2, 5, 15, 28, 41, 54, 106 and 108)
- Caregiver's quality of sleep at night (i.e., NOT the child's) during the study using the PSQI global score and components (at Weeks 0, 2, 5, 15, 28, 41, 54, 106 and 108)
- Dosage received by visit and maximum dosage received overall
- BMI and Z-score assessed during the study
- Pubertal assessment using the Tanner scale during the study. The Tanner scale will be used to assess and stage physical development in children ≥ 8 years of age. For children ≤ 5 years of age, only height and head circumference will be used to stage children development. Between the age of 5 and 8, the children's physical development will be determined using BMI.
- In children diagnosed with epilepsy, the number and severity of epilepsy seizures assessed during the study using seizures diaries completed by the parents at the time of the seizures

5 Study Design

This is a randomized placebo-controlled study in children diagnosed with Autism Spectrum Disorders and neurodevelopmental disabilities caused by neurogenetic diseases. Children will have a documented history of these disorders, as confirmed or consistent with the International Classification of Diseases (ICD-10) or Diagnostic and Statistical Manual of Mental Disorders, Fifth Edition, Text Revision (DSM-5/4) criteria, having International Classification of Sleep Disorders (ICSD) criteria-based sleep disturbances modified to take into account the uniqueness of insomnia in the pediatric population at screening.

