After the 4-week sleep hygiene (for children who do not have a documented history of sleep hygiene and behavioral intervention) and 2-week SB placebo run-in period, children who are still found eligible for study participation will be randomized in a 1:1 ratio to receive either Circadin® 2 mg or placebo for 3 weeks in a double-blind treatment period. After 3 weeks of treatment, on the last day of Week 5 \pm 3 days (Visit 3), sleep variables will be assessed to determine if dose modification (an increase to 5 mg) is required. Children will then continue on 2 or 5 mg of Circadin® or placebo for an additional double-blind period of 10 weeks. This double-blind period will be followed by an open-label period of 13 weeks. At the end of the 13-week open-label period on the last day of Week 28 \pm 3 days (Visit 5), sleep variables will be assessed to determine if a potential additional dose modification (i.e., an increase either to 5 mg for subjects who are still on 2 mg or an increase to 10 mg for subjects who are on 5 mg) is necessary. Children will continue at 2, 5, or 10 mg Circadin® in an open-label period for another 78 weeks of follow-up, which will include continuous safety monitoring and two efficacy assessment time points at Weeks 41 and 54. The study will end with a 2-week SB placebo run-out period.

6 Statistical Considerations

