12.1 Treatment Exposure

Details of study drug compliance, dose modifications and dose increases will be listed.

The time on treatment will be listed and summarized descriptively.

Time on treatment (days) in DB Phase = Last dose date of DB phase – first dose date of DB phase +1

Time on treatment (days) in OL Phase = Last dose date of OL phase – first dose date of OL phase +1

Time on active treatment (days) = Last dose date of active treatment – first dose date of active treatment +1

The number of subjects having a decrease in dose or an increase in dose will be tabulated by visit. % compliance will be summarized descriptively.

The dosage achieved (2/5/10mg) will be tabulated by scheduled visit and the maximum dose achieved will also be tabulated.

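### The cumulative active-treatment and final open-label AE tables give crude percentages over unequal observation time, with no rate per patient-time

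*SAP*

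**What the plan says.** SAP 12.3 tabulates the number of events and the number of children with an event, with percentages based on the size of the treatment group. It states: "Tables will be presented for the double blind and open-label phases separately". It then adds that "a cumulative summary will also be presented for all subjects on active treatment for all TEAEs", for SAEs and for events leading to discontinuation, covering either phase (Tables 14.3.2.14 to 14.3.2.16).

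SAP 9.2 states: "Unless otherwise specified, the two Open Label phases will be reported in the same table". At the main analysis the open-label tables hold Visit 5 data only; they are re-run with all data when the study ends. In SAP 16.1 the AE tables carry one undivided open-label title (for example Tables 14.3.2.3 and 14.3.2.5). Disposition (14.1.1.2 and 14.1.1.3) and concomitant medications (14.1.9 and 14.1.10) have separate tables for the first and second open-label phases.

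SAP 12.1 derives days on treatment in each of the double-blind and open-label phases and on active drug (the last begins "Time on active treatment (days) = Last dose date of active treatment"). These are listed and summarised on their own in Table 14.3.1.1. Neither document plans an AE incidence per patient-time, a time-to-first-event analysis, or AE tables by time interval.

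**The concern.** A percentage of children with an event has a clear meaning only for a stated period of observation. When the period lengthens, the percentage grows even if the underlying risk does not change.

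The cumulative active tables mix children with different planned time on drug, so their percentages belong to no single period. The final open-label tables run up to seven times as long as the double-blind phase, which is the only period with a placebo group. A reader who sets the two side by side cannot tell longer observation from a rising rate. A stable profile could look like deterioration, and a real increase could be dismissed as longer follow-up.

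This bears on a stated secondary objective, the evaluation of safety throughout the study (SAP 3.2), and on the second open-label phase, which exists as safety follow-up. Pooling across Visit 5 also puts weeks before and after 10 mg first becomes available into one column.

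**Working it through.** **Planned durations, from the documents**

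- Double-blind: 13 weeks. SAP 4.1: "TST time as assessed by a Sleep and Nap Diary after the 13-week, double-blind treatment period".
- First open-label: 13 weeks. SAP section 5: "This double-blind period will be followed by an open-label period of 13 weeks".
- Second open-label: 78 weeks. SAP section 5: "open-label period for another 78 weeks of follow-up".
- Total open-label: SAP 4.3 assesses "after 13, 26, 39, and 91 weeks of open-label treatment (Weeks 28, 41, 54, and 106, respectively". This reproduces: 106 − 15 = 91 and 13 + 78 = 91. The protocol's total duration also reproduces: 4 + 2 + 13 + 13 + 78 + 2 = 112 weeks.

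**Planned observation time behind each table**

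| Table | Week 28 report | Completion |
|---|---|---|
| Double-blind, each arm | 13 | 13 |
| Open-label | 13 | up to 91 |
| Cumulative active, randomised to Circadin | 13 + 13 = 26 | 13 + 91 = 104 |
| Cumulative active, randomised to placebo | 13 | 91 |

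**Crude percentage under constant risk, full follow-up**

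The documents give no AE rate, so 13-week incidences p of 5%, 10% and 20% are assumed. Crude percentage over w weeks = 1 − (1 − p)^(w/13).

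| p | 13 weeks | 26 weeks | 91 weeks | 104 weeks |
|---|---|---|---|---|
| 5% | 5.0 | 9.8 | 30.2 | 33.7 |
| 10% | 10.0 | 19.0 | 52.2 | 57.0 |
| 20% | 20.0 | 36.0 | 79.0 | 83.2 |

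For example, 1 − 0.9^7 = 52.2%. An equal mix of the two original arms in the cumulative table at p = 10% gives (10.0 + 19.0)/2 = 14.5% at Week 28 and (52.2 + 57.0)/2 = 54.6% at completion. The underlying rate is the same in every cell of a row: −ln(1 − p)/13 per week, or about 20.6, 42.3 and 89.6 first events per 100 patient-years.

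**With dropout**

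SAP 6.2 expects at least 90 of 120 children to reach Week 28 and at least 50 to complete the second open-label phase. Assume retention S(t) falls linearly from 1 at randomisation to 90/120 at 26 weeks and 50/120 at 104 weeks, so S(13) = 0.875. With weekly rate λ = −ln(1 − p)/13, the crude percentage from time a to b, per child present at a, is ∫ λ·exp(−λ(t − a))·S(t) dt / S(a).

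| p | Double-blind | Open-label at Week 28, per entrant | Final open-label, per entrant |
|---|---|---|---|
| 5% | 4.7 | 4.6 | 21.7 |
| 10% | 9.4 | 9.3 | 38.3 |
| 20% | 18.8 | 18.6 | 60.4 |

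From double-blind to final open-label the percentage rises by a factor of 21.7/4.7 = 4.6, 38.3/9.4 = 4.1 and 60.4/18.8 = 3.2, with no change in risk. Mean active exposure on the same pattern, for children randomised to Circadin versus ex-placebo entrants, is about 22.8 versus 12.1 weeks at Week 28, and 68.3 versus 64.1 at completion.

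**Which denominator a first-event rate needs**

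Dividing children with an event by the total time on treatment of SAP 12.1 would not repair this. In the full follow-up case at p = 10%, it gives 10/13 = 0.77 per 100 patient-weeks double-blind but 52.2/91 = 0.57 open-label. At p = 20% it gives 1.54 and 0.87. A constant risk would appear to fall by 25% to 44%, because time after the first event still counts in the denominator. First-event rates need time censored at the first event; total time suits event-count rates.

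**The case against.** The strongest defence is that the controlled comparison is sound. Both arms have 13 planned double-blind weeks and their AE tables are kept separate, so the Circadin-versus-placebo percentages are like for like. That stands. A reader might infer that unequal exposure biases the randomised safety comparison; the documents do not support that unless dropout differs between arms.

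Four further points carry weight:

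- **Timing.** In the Week 28 report both phase tables cover 13 weeks. The 91-week table appears only at completion, in what the SAP calls an appendix to the CSR and Protocol 12.3 calls a final CSR. This is correct, but the cumulative table is already unequal at Week 28 (26 against 13 weeks). Subtracting the Week 28 open-label table from the final one recovers event counts for the second phase. It does not recover numbers of children, since a child can have events in both.
- **TESS by visit.** SAP 12.2 plans TESS frequencies at each scheduled visit, which is a time-resolved view. It covers thirteen listed symptoms, not TEAEs or SAEs generally.
- **Exposure is reported.** Time on treatment is summarised and event counts are tabulated, so a reader could divide events by number of children times mean exposure. That approximates an overall event rate. It gives no first-event rate and does not separate the two open-label phases, because SAP 12.1 defines open-label time as one span.
- **Full follow-up is optimistic.** The 52% to 83% figures assume every child is followed for 91 or 104 weeks, although the documents expect a minimum of 50 of 120 to finish. The dropout calculation is the fairer guide, and there the rise is still three- to five-fold.

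**Conclusion.** The point holds for the cumulative active tables in both reports and for the open-label AE tables at completion. Their percentages mix or extend observation time, and no planned AE output corrects for it. At an assumed constant risk of 10% per 13 weeks, the final open-label figure would be about 38% under the assumed dropout pattern (52% with full follow-up), against about 9% (10%) in the double-blind table.

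These sizes rest on the assumed incidences, a constant rate, linear dropout through the expected completer numbers, and an open-label denominator of children who entered that phase. They show the mechanism and are not a forecast.

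A reader might also conclude that exposure is ignored altogether, or that long-term safety cannot be judged at all. Neither follows: exposure is summarised separately, and TESS by visit gives partial information. The gap is in how AEs are reported. It is worth closing before the tables are produced, and it does not affect the trial's design or its controlled comparison.

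**What to change.** Keep the crude tables and amend SAP 12.3 as follows.

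1. In the open-label and cumulative AE tables (including 14.3.2.14 to 14.3.2.16), add total patient-time and two rates:
   - events per 100 patient-years, using the SAP 12.1 time on treatment;
   - children with a first event per 100 patient-years at risk, with each child's time censored at the first event of that type, using AE start dates.
2. Split the final open-label AE tables at Visit 5 (open-label weeks 1–13 and 14–91), matching the split already planned for disposition and concomitant medications, and cut open-label time at the Visit 5 date for those columns.

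The double-blind tables can stay as they are, since planned exposure is equal. The cost is SAP wording, one extra derivation (time to first event, for which SAP 9.4 already has rules for partial AE dates) and extra table columns. No new data are needed.
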